Part A Usability Study: Cross-sectional study comparing outcome variables for stroke survivors with varying levels of motor deficit impairment in their upper extremity. Subjects with mild motor deficits will be compared against stroke survivors with severe motor deficits after completing exercises with both commercial and custom therapy devices. Therapy exercises will be performed in random order, decided prior to the session. It will be randomly determined which robot the patient will use first, the order of operating modes used for the new robot, and the order of therapy exercises performed in each mode. Surface Electromyography (EMG) will be used in order to detect the small electric currents, or signals, which are generated by muscle activity. The collection of the strength and pattern of the signals will permit us to verify muscle activity over time. Part B Therapy Study: Pre-post study looking at change in outcome variables over 12 therapy sessions (three times a week for one month). Only low and mid functioning stroke survivors will be asked to participate in Part B of the study, and only the custom haptic device will be used by the study subjects. Pre-post evaluations will be administered at session 1 and 12. Surface Electromyography (EMG) will be used in order to detect the small electric currents, or

signals, which are generated by muscle activity. The collection of the strength and pattern of the signals will permit us to verify muscle activity over time.

Study duration

1) We estimate that it will take 3 years from the date of IRB approval to enroll all subjects and complete the study. 2) Part A - The subject's participation in the study will be limited to approximately 4 hours; 1-2 hours to be evaluated by a therapist with expertise in stroke rehabilitation and 2-3 hours of assessing the viability and usability of the various therapy devices. Part B - Subjects enrolled in Part B will be asked to return 3 times a week for 1 month (12 sessions). All sessions will last approximately 1.5 hours. 3) Projected date of the proposed study: 3/1/14 to 7/1/17.

Resources necessary for human research protection

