Describe research staff and justify that the staff are adequate in number and qualifications to conduct the research. Describe how you will ensure that all staff assisting with the research are adequately informed about the protocol and their research related duties. Please allow adequate time for the researchers to conduct and complete the research. Please confirm that there are adequate facilities for the research.

All staff have taken the human subject certification and HIPAA training. The PI will have regular meetings with the research team to ensure that the team is adequately trained. We will recruit from our therapy services.

Characteristics of the Study Population

Target population

Stroke survivors greater than 18 years of age with hemiplegia and varying levels of impairment.

Subjects enrolled by Penn Researchers

56

Subjects enrolled by Collaborating Researchers

0

Accrual

Various Penn and Good Shepherd Penn Partners (GSPP) databases will allow the research team to search the respective systems within the parameters of the inclusion/exclusion criteria. Given the number of stroke survivors over the age of 18 with hemiplegia served by the Penn and GSPP community, recruitment of 56 (total for parts A, B) stroke survivors three months post event should be obtainable within the time frame specified. Justification for the sample size is based on the fact that this is a pilot study. Also, we expect that in Part A, not all willing participants will be able to continue post evaluation by a therapist (more than mild depression or cognitive impairment will be detected). Ideally, all low-functioning stroke subjects who participated in Part A would participate in B; however, we expect some attrition from the original group, requiring more subjects to be recruited. Subjects may also participate in Part A.

Key inclusion criteria

Part A: Stroke survivors greater than 18 years of age with hemiplegia and varying levels of impairment. The subject's stroke must have occurred at least 3 months prior to enrollment in the study. Part B: Low-functioning stroke survivors greater than 18 years of age with hemiplegia. The subject's stroke must have occurred at least 3 months prior to enrollment in the study.

Key exclusion criteria

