
Subjects will be given a 15 minute break. 4) First Therapy Device: Subjects will be introduced to several robots: a wheel, joystick, and custom crank chosen randomly (like the flip of a coin). First, they will be trained in the use of all robots and their safety features. Following training, they will be asked to move each robot into different positions, first without pressure applied to the handle, and then with pressure applied to the handle. After each exercise they will be asked about their level of exercise and level of pain discomfort. After subjects finish all exercises with a robot, they will be given a survey about the robot. They will also be given surveys to discuss their experience with the device and their level of motivation for use of them. The surface EMG may be utilized during the entirety of the participant's interaction with the novel therapy device. Prior to its placement on the subject, the reason for its use will be thoroughly explained. 5) Break: Subjects will be given a 15 minute break. 6) Subsequent Therapy Device: Subjects will be instructed in the use of another robot. The same procedure will be followed as in the first evaluation. The surface EMG may be utilized during the entirety of the participant's interaction with the novel therapy device. Prior to its placement on the subject, the reason for its use will be thoroughly explained. 7) Final Survey: Subjects will be given a survey asking them to evaluate the robots and indicate which robot they prefer. Part B: For subjects invited to participate in Part B of the study - only low functioning stroke survivors are eligible - participation in this part of the study will include the following steps: 1) Informed Consent: After arrival, subjects will review and sign the consent form with study personnel present. 2a) Pre-Assessments: If subjects are only participating in Part B of the study, at their first visit, a member of the research team will evaluate their affected arm and assess their ability to use it. Subjects will be evaluated using a battery of assessments in order to determine their level of impairment such as the Beck Depression Inventory, Upper Extremity Fugl-Meyer, Montreal Cognitive Assessment, Jebson Taylor, Box in Block, Modified Ashworth, and grip strength using a dynamometer, etc. If a study subject participated in Part A, they will not be reevaluated by a therapist. 2b) Workspace Assessment: Same as in Part A 2) Custom Therapy Device: Subjects will be introduced to the custom robot. They will be trained in the use of this robot and its safety features (1st session). Following training, they will be asked to move the robot into different positions. After each exercise subjects will be asked about their level of exercise and level of pain discomfort. Subjects will continue to work with the custom therapy device for 12 sessions over the course of one month. The surface EMG may be utilized during the entirety of the participant's interaction with the novel therapy device. Prior to its placement on the subject, the reason for its use will be thoroughly explained. 3) Motivation Questionnaire: At the end of their 1st and 12th sessions, subjects will be asked to complete a questionnaire assessing their level of motivation. 4) Post-Study Survey: After their last session, subjects will be asked to complete a survey assessing the robot. 5) Post-Study Assessment: After their last session, a certified therapist will evaluate the participants' affected arm and assess their ability to use it. In addition, they will also be evaluated for depression and a mental health assessment will be given.

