
The following documents are currently attached to this item:

There are no documents attached for this item.

Deception

Does your project use deception?

No

Analysis Plan

1) Clinical data will be analyzed to determine how subjects low versus high function perform on metrics developed using the robots. 2) Trajectory tracking using a baseline with zero resistance will be established for each patient. The root mean square metric will be used to assess accuracy in tracking tasks and subjects' performance across groups (low versus high) and devices in Part A, and across time in Part B. Using a 2-way ANOVA test for Part A, and an alpha of 0.05, significant difference across groups will be detected. A paired t-test, and an alpha of 0.05, will detect significant difference across time pre-post the 12 sessions. 3) Data collected from the surface EMG will be analyzed to verify muscle activity over time. 4) Data results will be used to build a simulation model of the human-robot tracking and determine a prediction of the joint and muscle forces that are used in Part A and Part B. 5) Data collected with the kinect will be assessed for kinematic and dynamic workspace. The data will be fitted to a computerized model of the upper limb to extract forces and positions defining dynamic and kinematic workspace.

The following documents are currently attached to this item:

There are no documents attached for this item.

Are you conducting research outside of the United States?

No

Data confidentiality

x Paper-based records will be kept in a secure location and only be accessible to personnel involved in the study.

x Computer-based files will only be made available to personnel involved in the study through the use of access privileges and passwords.

Prior to access to any study-related information, personnel will be required to sign statements agreeing to protect the security and confidentiality of identifiable information.

x Wherever feasible, identifiers will be removed from study-related information.

A Certificate of Confidentiality will be obtained, because the research could place the subject at risk of criminal or civil liability or cause damage to the subject's financial standing, employability, or liability.

A waiver of documentation of consent is being requested, because the only link between the subject and the study would be the consent document and the primary risk is a breach of confidentiality. (This is not an option for FDA-regulated research.)

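### Design and Procedures conflict on the Part B baseline; if Part A scores are carried forward, regression to the mean is counted as improvement on the classifying score

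*Combined protocol and SAP*

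**What the plan says.** All references are to the combined protocol and SAP.

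- **Who enters Part B.** Procedures: "only low functioning stroke survivors are eligible". Key inclusion criteria: "Low-functioning stroke survivors greater than 18 years of age with hemiplegia". Study Design is wider: "Only low and mid functioning stroke survivors will be asked to participate in Part B of the study". No section names a classifying instrument or a cut-off.
- **How function is assessed.** Procedures, step 2a of both parts: "Subjects will be evaluated using a battery of assessments in order to determine their level of impairment". The battery includes the upper extremity Fugl-Meyer and grip strength, both listed under Primary outcome variable(s).
- **Route from Part A.** Accrual: "Ideally, all low-functioning stroke subjects who participated in Part A would participate in B".
- **When the 'pre' is taken.** Study Design: "Pre-post evaluations will be administered at session 1 and 12". Procedures, Part B, step 2a: "If a study subject participated in Part A, they will not be reevaluated by a therapist".
- **Analysis.** Part B has one group and one device. Analysis Plan item 2 applies a paired t-test at alpha 0.05, which "will detect significant difference across time pre-post the 12 sessions". That item is about root mean square tracking accuracy. No pre-post test is named for Fugl-Meyer or grip.

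**The concern.** Under the Procedures, a subject who comes from Part A has only one clinical evaluation before treatment, the Part A battery. The same battery is the only described means of finding that the subject is low-functioning. A score that was low partly through measurement error or a bad day makes entry more likely, and it tends to be higher on the next measurement even if the subject has not changed. With no control group and no second baseline, that rise is read as benefit.

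The bias favours improvement on the score that drives the classification, and it arises even in fully stable subjects. It bears on the Abstract's second purpose, which is to learn whether low-functioning patients benefit and by how much. Under the Design's session-1 evaluation the problem would not arise for Part A entrants, so everything turns on which of the two sections is followed.

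**Working it through.** **The plan's own figure.** There is none to reproduce. The 56 subjects (about 36 in the Abstract) are justified only as a pilot, with no effect size, SD, power or separate Part B number.

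**Assumptions, none from the documents.** Normal scores; test-retest reliability ρ of 0.80 to 0.98; share classed as eligible f of 1/3, 1/2 or 2/3 (the last standing for low and mid function); Part B n = 20; two-sided test; no true change.

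**Expected false gain.** If subjects are selected below a cut-off c on one score and that score is reused as 'pre':

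mean change = (1 − ρ) × SD × φ(c)/Φ(c)

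The factor φ(c)/Φ(c) is 1.091 for f = 1/3, 0.798 for f = 1/2 and 0.545 for f = 2/3. At ρ = 0.80 and f = 1/2, for example, the gain is 0.20 × 0.798 = 0.160 SD. At ρ = 0.90 and f = 1/3 it is 0.10 × 1.091 = 0.109 SD. SD is that of the unselected population.

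**Gain in SD, and type I error of the paired t-test (simulated, about 20,000 trials per cell, n = 20):**

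| Selected on one score | ρ = 0.80 | ρ = 0.90 | ρ = 0.95 | ρ = 0.98 |
|---|---|---|---|---|
| Lowest third | 0.22; 33% | 0.11; 19% | 0.05; 11% | 0.02; 7.5% |
| Lowest half | 0.16; 19% | 0.08; 12% | 0.04; 8.3% | 0.016; 6.1% |
| Lowest two-thirds | 0.11; 11% | 0.055; 8.0% | 0.027; 6.5% | 0.011; 5.8% |

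Repeat runs put the top-left error rate at 32% to 33%.

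**Other ways of classifying.**

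- *Average of four battery items* (assumed true-score correlation 0.6, independent errors, lowest half, n = 20): type I error on one item is about 5.0%, 4.8%, 5.5% and 6.6% at ρ = 0.97, 0.95, 0.90 and 0.80. An error shared by all items on the day would raise these.
- *One item classifies and another is tested* (for example Fugl-Meyer and grip, independent errors): about 5% at every reliability.

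**Baseline re-measured after selection.** Mean change is about 0.00 SD and type I error is 4.7% to 5.2% in every single-score scenario.

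**The case against.** Four points weigh on the other side.

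1. *The Design already schedules a session-1 evaluation, and the Procedures rule out only re-evaluation by a therapist.* This stands as far as it goes. The documents do not say that the Part A score is carried forward; that follows only if the Procedures sentence governs. What can be shown is a conflict with a consequence, not a stated rule.
2. *Selection on the battery is inferred.* This is correct. For Part-B-only recruits it matters most: they are invited and consented before the battery is given, and are found through databases, referral and phone screening. If they are classified before the battery, it produces little or none of this bias. The Part A route is better supported, because Accrual sends subjects already known to be low-functioning into Part B.
3. *The paired t-test sits with tracking error, which is not a battery item.* This also stands. A reader might infer that the planned test on tracking error has a false-positive rate of 20% or 30%. The documents do not support that, since regression to the mean reaches tracking error only through its correlation with the battery. The rates above apply to a paired t-test on a classifying score.
4. *The larger rates need one classifying score and tight selection.* This is true. A reader might also infer that Fugl-Meyer and grip are both biased by the amounts in the table. They are not, if one score classifies and the errors are independent. Composite classification, or admitting low and mid function with a reliable score, brings the rate to about 5% to 6%.

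**Conclusion.** The concern holds for the Part A route, conditionally. Study Design and Procedures conflict on whether Part A entrants get a fresh clinical baseline. If they do not, the score that classed them as low-functioning also serves as their 'pre', and regression to the mean is counted as improvement in a comparison with no control.

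The size cannot be determined from the documents. With n = 20 and reliability of 0.80 to 0.97, all assumed, the type I error of a paired t-test on the affected outcome runs from about 5% to about 32–33%. The low end is composite classification, or selection of low and mid function with high reliability. The high end is a single score, the lowest third and reliability 0.80. If only some entrants carry a score forward, the excess is diluted.

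It would be too strong to say that the plan selects all Part B subjects on their 'pre' score, since no section states a classifying instrument or cut-off.

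**What to change.** - Reconcile Study Design with Procedures, Part B, step 2a: delete the no-re-evaluation sentence as it applies to the outcome measures. For Part A entrants, use the Part A battery only to classify function and the session-1 evaluation, which the Design already schedules, as 'pre'.
- For Part-B-only recruits, fix eligibility before the baseline battery is scored as 'pre'.
- Name the instrument and cut-off that define functional level, and reconcile the low-only text with the low-and-mid text.

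The cost is protocol wording, one repeat battery at session 1 for each Part A entrant, and slightly smaller apparent gains. The change removes regression to the mean but not natural recovery, which is possible with entry from 3 months after stroke, or practice effects. Change in Part B would still not be attributable to the device without a concurrent control.

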The primary outcomes are motor control, as measured by the upper extremity Fugl-Meyer; ADL function; and grip strength as measured by a dynamometer; a custom metric to determine Kinematic workspace and dynamic workspace will be employed. Customized metrics will be defined such as movement time, movement velocity, and accuracy. New outcome variables related to MRI: fiber density and hemisphere activation

Secondary outcome variable(s)

The secondary variables for motor impairment are upper extremity coordination, finger dexterity, and spasticity - the Box and Block and Ashworth assessments will be used to evaluate these.

Background

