Part A: Participation in this part of the study will include the following steps: 1) Informed Consent: After arrival, subjects will review and sign the consent form with study personnel present. 2a) Pre-Assessments: A member of the research team will evaluate the subjects' affected arm and assess their ability to use it. Subjects will be evaluated using a battery of assessments in order to determine their level of impairment such as the Beck Depression Inventory, Upper Extremity Fugl-Meyer, Montreal Cognitive Assessment, Jebson Taylor, Box in Block, Modified Ashworth, and grip strength using a dynamometer, etc. 2b) Workspace Assessment: The protocol for the kinematic workspace would entail of moving patients upper extremity in a series of motions that mark the key points of their workspace. This would include movement with extended elbow to manipulate the shoulder joint in the cardinal directions (e.g. horizontal movements at the abdominal and shoulder levels, and vertical movements at 0, 45, 90 and 135 degrees), internal/external rotation of the shoulder, as well as functional movements of the arm. For the functional movements the patient would be asked to touch six points on their body, the left and right sides of their hips, their left and right shoulders, their mouth and the top of their head while being monitored by a Kinect camera. These actions are chosen as they cover areas necessary for ADLs such as eating, grooming and toileting and covers motion in clinically relevant planes. Each participant would be also given the standard clinical score. The movement protocols would be repeated under a loading condition where light weights (0.5-1lb) would be attached to subjects wrist. Given the additional mass, we would determine the change in the kinematic workspace space as well as the change in the joint torques. The protocol for recovery of dynamics would entail of the a series of motions using the TheraDrive systems as described in Theriault, A., Nagurka, M., Johnson, M.J: Therapeutic Potential of Haptic TheraDrive: An Affordable Robot/Computer System for Motivating Stroke rehabilitation, in: 5th IEEE RAS&EMBS International Conference, pp.415-420, 2014. The TheraDrive would be positioned at various locations in the subjects workspace (e.g. closer to the torso, away from the torso, higher/lower). The ability to exert specific torques at these locations would provide information on the dynamic capacity of the muscles within various points of the workspace. 3) Break:

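### Part B subjects who come from Part A skip the session-1 clinical battery, so their Fugl-Meyer and grip change has no session-1 value and no named baseline

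*Combined protocol and SAP*

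**What the plan says.** Under Study Design, the protocol describes Part B as a pre-post study over 12 sessions in which only the custom device is used. On timing it says: "Pre-post evaluations will be administered at session 1 and 12". No exception is made.

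Under Procedures, Part B step 2a is narrower: "If subjects are only participating in Part B of the study, at their first visit, a member of the research team will evaluate" the affected arm. The step then exempts everyone else: "If a study subject participated in Part A, they will not be reevaluated by a therapist". The assessment in question is the same "battery of assessments in order to determine their level of impairment such as the Beck Depression Inventory, Upper Extremity Fugl-Meyer" (and others, including grip strength) that Part A uses in its own step 2a. Part B step 5 requires an arm evaluation by a certified therapist after the last session and exempts nobody.

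The section on primary outcome variables states: "The primary outcomes are motor control, as measured by the upper extremity Fugl-Meyer; ADL function; and grip strength as measured by a dynamometer", followed by workspace and customized metrics.

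On who moves from one part to the other, the Accrual section says: "Ideally, all low-functioning stroke subjects who participated in Part A would participate in B". It also says: "we expect some attrition from the original group, requiring more subjects to be recruited".

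**The concern.** Staff cannot follow both the Design section and step 2a for a subject who has been through Part A. If they follow step 2a, that subject has a clinical score after session 12 and none from the battery at session 1.

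The natural substitute is the Part A score, but it is a different kind of pre value. It was taken before the Part A robot exercises and at an unspecified distance from Part B. Ongoing rehabilitation is barred only for those enrolled in Part B (Key exclusion criteria, item 4), so therapy between the two parts is not excluded. Change from a Part A score would mix the 12 sessions with whatever happened in that interval. Direct entrants have no such interval.

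Part B has no control arm, so nothing else in the design separates the two. Two named primary outcomes are affected, on the entry route that the Accrual section treats as the ideal one.

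**Working it through.** **1. The texts side by side**

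| Item | Direct entrant to Part B | Subject from Part A |
|---|---|---|
| Design section, session 1 | evaluated | evaluated |
| Part B step 2a, first visit | evaluated | not re-evaluated |
| Part B step 5, after last session | evaluated | evaluated |
| Earlier score from the same battery | none | Part A step 2a |
| Rule naming that score as baseline, or limiting its age | not needed | none found |

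The only baseline in the Analysis Plan (item 2) is robot tracking at zero resistance, which is not a clinical score.

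**2. How old the Part A score could be**

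Study duration, item 3, gives: "Projected date of the proposed study: 3/1/14 to 7/1/17". From 1 March 2014 to 1 July 2017 is 36 + 4 = 40 months. Less about one month of Part B sessions, a gap of up to about 39 months would fit in that window. This is a projection and not a cap, and actual gaps could be days. The documents set no limit.

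**3. Bias in mean clinical change**

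Let *p* be the share of Part B subjects who come from Part A and *d* their mean drift between the Part A battery and session 1. If the Part A score is the pre value:

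bias = *p* × *d*

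Neither quantity is in the documents. With *p* = 0.5 and *d* = 2 points (assumed), the bias is 0.5 × 2 = 1 point. With *d* = 0 it is zero.

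**4. What that could do to a test (illustration only)**

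Assumptions: no true effect of the 12 sessions; a one-sample t-test on change scores (that is, a paired t-test), two-sided at 0.05; a fixed number of the *n* subjects shifted by *d*; 1,000,000 simulated trials per cell. The SD of change, *d*, *p* and *n* are all assumed.

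| SD | Share *p* | Drift *d* | Bias *p* × *d* | Rejection, n=10 | Rejection, n=20 |
|---|---|---|---|---|---|
| 5 | 0.5 | 0 | 0 | 0.050 | 0.050 |
| 5 | 0.5 | 1 | 0.5 | 0.058 | 0.070 |
| 5 | 0.5 | 2 | 1.0 | 0.082 | 0.128 |
| 5 | 0.2 | 2 | 0.4 | 0.053 | 0.060 |
| 5 | 0.3 | 2 | 0.6 | 0.059 | 0.076 |
| 5 | 0.8 | 2 | 1.6 | 0.143 | 0.266 |
| 3 | 0.5 | 2 | 1.0 | 0.133 | 0.258 |
| 8 | 0.5 | 2 | 1.0 | 0.062 | 0.081 |

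The rates run from the nominal 5% to about 27%. They show how the problem scales and do not estimate its size in this trial.

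**The case against.** **Carrying the Part A score forward is the obvious intent, so no data are missing.** This is probably the intent, and these subjects do have earlier Fugl-Meyer and grip values. But no section says so, none limits the age of the score, and the Design section says session 1. The defect is a pre value with no defined time.

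**The exemption refers only to a therapist, so other staff could repeat the battery.** The wording leaves a little room for this. However, step 2a itself confines the battery to subjects who take part in Part B alone, and the Study duration section describes the Part A evaluation as a therapist's.

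**Step 2b repeats the Part A workspace assessment, which mentions a standard clinical score.** That score is undefined and is not tied to Fugl-Meyer or grip. Read as the full battery, it would contradict step 2a.

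**The paired t-test belongs to the tracking metric.** This stands. The test in Analysis Plan item 2 follows the root mean square tracking measure and is not explicitly tied to clinical scores. The rejection rates above therefore describe a test the plan does not clearly specify, and the severity of the point does not rest on them. The bias in mean change arises whatever test is used.

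**This is a pilot and few subjects may be affected.** The affected share is indeed unknown, because the Accrual section expects attrition and new recruits. But the carry-over route is planned, and it is not an edge case.

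**Conclusion.** The point holds. The Design section and Part B step 2a contradict each other. Following step 2a leaves carry-over subjects without a session-1 value on two primary outcomes of a single-arm pre-post study. This finding rests on the text alone and needs no assumed figure.

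The size of any bias cannot be determined: it is the carry-over share times the drift, of unknown sign, and could be zero. Only within-subject clinical change is affected. Robot tracking and the workspace assessment have no such exemption. The point should be fixed, because the correction is small and primary outcomes depend on it.

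**What to change.** Reconcile the two sections. Delete the exemption sentence in Part B step 2a and replace the step's opening with wording such as:

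*Every Part B subject, including those who took part in Part A, completes the upper-limb outcome battery (Upper Extremity Fugl-Meyer, Jebson Taylor, Box and Block, Modified Ashworth, grip strength) at session 1, before the first robot exercise. This value is the pre value for Part B.*

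The Beck and Montreal assessments are left out because neither is a named outcome.

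For carry-over subjects already treated without a session-1 battery, report clinical change by entry route and give the interval from the Part A battery to session 1. This needs no new measurements.

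Naming the Part A score as baseline, with a maximum interval and a sensitivity analysis by source of baseline, would also make the text consistent. It is second best, because the interval stays inside the change score.

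**Cost.** A short amendment and one repeat of an existing battery per carry-over subject, with no extra subjects. The downside is a longer first Part B visit. The Study duration section allows 1-2 hours for the whole Part A therapist evaluation and about 1.5 hours for each Part B session, while the exclusion criteria ask Part B subjects to sit upright for 2 hours at a time. Direct entrants already complete the battery at their first visit, so the same scheduling question already exists for them.

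### Part A tests low versus high function with no score, cut-off or rule for intermediate subjects, and does not use the severity score already collected to predict tracking error

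*Combined protocol and SAP*

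**What the plan says.** **Analysis.** Analysis Plan item 2 assesses root-mean-square tracking error "across groups (low versus high) and devices in Part A". The test is given as follows: "Using a 2-way ANOVA test for Part A, and an alpha of 0.05, significant difference across groups will be detected". Item 1 uses the same two groups: "Clinical data will be analyzed to determine how subjects low versus high function perform on metrics developed using the robots".

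**Design.** The Design section states the Part A contrast by its two ends: "Subjects with mild motor deficits will be compared against stroke survivors with severe motor deficits".

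**Recruitment.** Key inclusion criteria admit the whole range: "Part A: Stroke survivors greater than 18 years of age with hemiplegia and varying levels of impairment". No quota by level is set and the middle is not excluded.

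**A third level.** The Design section says of Part B: "Only low and mid functioning stroke survivors will be asked to participate in Part B of the study". This is the only place where a mid level is named. Key inclusion criteria and Procedures both restrict Part B to low-functioning subjects.

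**How level is set.** Procedures, Part A step 2a, says that a battery of tests will establish the level of impairment. The battery includes the upper-extremity Fugl-Meyer and comes before any device step. No score or threshold is tied to low, mid, high, mild or severe. The Fugl-Meyer is also a primary outcome. The Analysis Plan does not name it as the grouping variable or as a covariate.

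**The concern.** Group is one of the two factors in the only Part A hypothesis test, and how low-functioning patients fare is a stated purpose of the study. Yet two analysts following the plan could form different groups from the same data. An intermediate subject might be left out, joined to the low group or joined to the high group.

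Two things are at stake:

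- **Precision.** Cutting a graded severity measure in two discards information, and a small pilot has little to spare.
- **Error control.** A cut that is not written down can still be moved once tracking results are known, and the nominal 0.05 level then no longer holds.

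**Working it through.** The plan gives no power, effect size or standard deviation, so there is no figure of its own to reproduce. What follows only illustrates the size.

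**Inputs from the document.** Two groups and alpha 0.05 (Analysis Plan). About 36 subjects (Abstract). 56 subjects for Parts A and B together (Accrual). The number in Part A alone is not given, so both totals are shown.

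**Assumptions.** Severity x is standard normal, tracking error is linear in x with constant variance, there is one averaged value per subject, and tests are two-sided.

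**Efficiency relative to the continuous score.** The slope on x has information proportional to N. If two groups of sizes n1 and n2 have mean scores δ apart, their comparison has information proportional to δ² / (1/n1 + 1/n2). The normal density at the point that cuts off the upper third (0.431) is 0.3636.

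- Median split: δ = 2√(2/π) = 1.596, so δ²/4 = 2/π = 0.637.
- Middle third dropped: the mean of the upper third is 0.3636 / (1/3) = 1.091 and δ = 2.182, so δ²/6 = 0.793.
- One third against the other two: δ = 0.3636 / (1/3 × 2/3) = 1.636, so δ² × 2/9 = 0.595.

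In effective numbers, in the same order: 36 subjects act like 22.9, 28.6 and 21.4; 56 act like 35.7, 44.4 and 33.3. Dropping the middle third removes about 12 of 36, or about 18 of 56.

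**Power** (simulation, 20,000 replicates per setting; r is the assumed correlation between severity and tracking error):

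| N | r | Continuous | Median split | Mid third dropped | Low third vs rest |
|---|---|---|---|---|---|
| 36 | 0.3 | 0.43 | 0.29 | 0.33 | 0.26 |
| 36 | 0.4 | 0.69 | 0.49 | 0.56 | 0.45 |
| 36 | 0.5 | 0.89 | 0.70 | 0.78 | 0.66 |
| 36 | 0.6 | 0.98 | 0.88 | 0.93 | 0.85 |
| 56 | 0.3 | 0.62 | 0.43 | 0.50 | 0.41 |
| 56 | 0.4 | 0.88 | 0.68 | 0.77 | 0.66 |
| 56 | 0.5 | 0.98 | 0.88 | 0.94 | 0.86 |
| 56 | 0.6 | 1.00 | 0.98 | 0.99 | 0.97 |

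The cost is about 5 to 24 points of power at N = 36 and about 1 to 22 points at N = 56.

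**False positives if the cut is moved** (simulation, no true effect, 40,000 replicates, nominal 5%). Taking the best of three placements of the middle third (dropped, joined to low, joined to high) gives about 10% at either N. Taking the best cut anywhere within the middle third gives about 18% at N = 36 and 18% to 20% at N = 56, depending on how 56 is divided into thirds. This is what an unwritten rule allows. It does not predict what will be done.

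**Effect of enrolment at the ends.** If half the subjects shared one low score and half one high score, group and score would carry the same information and nothing would be lost. The nearer Part A comes to that, the smaller the loss.

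**The case against.** A reader might infer three stronger things. The document does not support them.

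- **That a mid group is recruited into Part A and has no cell.** The mid level is named only for Part B, and two other sections contradict even that. Intermediate subjects in Part A are inferred from the broad inclusion criterion. With no cut-off given, low versus high may simply divide everyone.
- **That the cut will be chosen after the data are seen.** The battery that establishes level precedes all device use, and inviting subjects to Part B needs some working definition of low function. A late cut is a risk left open, not a documented plan.
- **That Fugl-Meyer information is thrown away.** It is kept as a primary outcome, and nothing says that the groups derive from it; it is one test in a battery. What is missing is its use as a graded predictor of tracking error.

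There are also objections of substance. The study is a pilot with no power claim to undermine. Linearity is not established, and the Abstract's hypothesis that low-functioning patients gain most would fit a threshold pattern. The Design section asks a group question, which a slope does not answer in the same terms.

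These points stand. They make the efficiency figures illustrative and justify keeping the group contrast in the report. They do not supply the missing grouping rule, and pilot status does not remove the need for one when the plan tests at 0.05.

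**Conclusion.** The concern holds in limited form. The only Part A test rests on a two-level factor with no defining score, cut-off or place for intermediate subjects, and a graded severity measure taken before device use is not used as a predictor. Under a normal score and a linear relation, two groups keep about 59% to 79% of the information in the continuous score. The true loss is unknown because the Part A sample size, the distribution of severity and the shape of the relation are not given. It would be smaller if enrolment favours the two ends. This is an inexpensive improvement to the analysis and does not invalidate the study.

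**What to change.** 1. In the Part A tracking-error model, replace the two-level factor with the pre-device upper-extremity Fugl-Meyer as a continuous term, together with its interaction with device. Include every subject, and allow for each subject using more than one device.
2. Plot tracking error against the score for each device to check that a straight line is adequate.
3. Report low versus high as a supporting summary, so that the contrast stated in the Design section is kept. Before analysis, write down the score that defines the groups, the cut-offs and where intermediate subjects go.
4. Reconcile the Design section with Key inclusion criteria and Procedures on whether mid-functioning subjects may enter Part B, and state the sample size intended for Part A.

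The cost is analysis wording, with no new measurements or visits. The downside is the assumption of an approximately linear relation. If the plot contradicts it, the pre-specified group summary remains.
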